# Preparation and conduct of the MMTT

The MMTT will be initiated in the morning after fasting for at least 6 hours. The NNC0114-0006/placebo may be given during the MMTT.

Subjects will be instructed not to take basal insulin after 22.00 the evening before the MMTT. Receipt of insulin boluses is allowed until 2 hours prior to the MMTT.

Protocol		Date:	07 May 2015	Novo Nordisk
Trial ID: NN9828-4150	CONEIDENTIAL	Version:	2.0	
UTN: U1111-1154-7172	CONFIDENTIAL	Status:	Final	
EudraCT no.: 2014-001215-39		Page:	54 of 141	

The plasma glucose value measured at the site before the MMTT must be  $\leq 9.0 \text{ mmol/l}$  (162 mg/dl) in order to avoid hyperglycaemia during the MMTT. Therefore if the plasma glucose value measured at the site is > 9.0 mmol/l (162 mg/dl) the subject may receive bolus insulin and the MMTT can be performed after 2 hours if a plasma glucose value  $\leq 9.0 \text{ mmol/l}$  (162 mg/dl) is confirmed. The MMTT may also be re-scheduled within 1-10 days. Re-scheduling of the MMTT is not considered as an unscheduled visit. Two rescheduling's are allowed per MMTT visit. If this is not possible the MMTT must be reported as not done. All other assessments at the visit should be conducted as planned including dosing of NNC0114-0006/placebo.

If plasma glucose value measured at the site before the MMTT is  $\leq$ 3.9 mmol/l (70 mg/dl), the MMTT will be rescheduled within 1-10 days. Re-scheduling of the MMTT is not considered as an unscheduled visit. Two rescheduling's are allowed per MMTT visit. If this is not possible the MMTT must be reported as not done. All other assessments at the visit should be conducted as planned including dosing of NNC0114-0006/placebo.

All plasma glucose values to be measured at site must be measured with a validated BG instrument. The BG meters handed out to the subjects should not be used for this purpose.

The subject's body weight must be measured before intake of the standardised liquid meal. The standardised liquid meal will be provided by Novo Nordisk. The subject must consume 6 ml/kg (maximum 360 ml) of the standardised liquid meal as quickly as possible and within 12 minutes. The investigator should confirm that the subject consumed the required amount in the eCRF.

Blood samples (11-point profile) will be collected 10 minutes prior to the meal (-10) at meal start (0), and at 15, 30, 60, 90, 120, 150, 180, 210 and 240 minutes after meal start. The blood samples will be assayed for C-peptide and plasma glucose. During the MMTT plasma glucose will be monitored on a validated plasma glucose instrument. If the glucose level exceeds 16.7 mmol/l (300 mg/dl) plasma ketones (betahydroxybutyrate) should be measured on a BG meter.

The subject is allowed to go to the toilet. The number of visits to the toilet should be limited. The subjects are allowed to drink water 2 hours after start of the MMTT. The amount of ingested water should be limited.

#### Precautions during the MMTT

In case the plasma glucose exceeds 16.7 mmol/l (300 mg/dl) and plasma ketones > 0.6 mmol/l and  $\leq$  1.5mmol/l (only measured if plasma glucose is above 16.7 mmol/l (300 mg/dl)), the MMTT can be stopped at the discretion of the investigator and rescue insulin treatment may be initiated if deemed necessary.

Protocol E   Trial ID: NN9828-4150 V   UTN: U1111-1154-7172 CONFIDENTIAL   EudraCT no.: 2014-001215-39 P	Date: 07 May 2015   Version: 2.0   Status: Final   Page: 55 of 141	Novo Nordisk
--	--	--------------

If the plasma ketone level is above 1.5 mmol/l presenting a risk of ketoacidosis, the MMTT **must** be stopped and appropriate treatment should be initiated. The plasma ketone level should be controlled as long as it is above 1.5 mmol/l.

In case of hypoglycaemia during the MMTT (plasma glucose value <3.9 mmol/l (70 mg/dl)), the MMTT can be stopped at the discretion of the investigator and rescue treatment according to local practice can be initiated.

#### After the MMTT

The subjects may have a meal after the last blood sample has been taken.

It is up to the discretion of the investigator to decide if subjects who normally takes basal insulin in the morning should take their basal insulin after the MMTT. Bolus insulin will be allowed jointly with the post-test meal, as applicable.

#### **Documentation of the MMTT**

The following has to be recorded:

- Date of mixed meal tolerance test
- Was the subject fasting prior to intake of liquid meal (Y/N)
- Did the subject withhold the insulin treatment as required prior to the MMTT (Y/N)
- Was the last SMPG measurement at the site before start of the meal within the acceptable range (4.0-9.0 mmol/l)
- Code number(s) of the liquid meal
- Meal time. Actual time for the start and stop
- How much volume of the liquid meal was ingested (ml)
- Actual time points for the blood samples
- Was the MMTT stopped prematurely and reason for stopping

#### 8.3.2 Self-measured blood glucose

At Visit 2, subjects will be provided with a BG meter including lancets, plasma-calibrated test strips and control solutions as well as instructions for use (control solutions will only be provided if they are needed, requested or required according to local requirements or procedures). The subjects will be instructed in how to use the device, the instruction will be repeated as necessary during the trial.

The blood glucose meter use test strips calibrated to plasma values. Therefore, all measurements performed with capillary blood are automatically calibrated to plasma equivalent glucose values, which will be shown on the display.

Protocol Trial ID: NN9828-4150 UTN: U1111-1154-7172 FudraCT no : 2014-001215-39	CONFIDENTIAL	Date: Version: Status: Page:	07 May 2015 2.0 Final 56 of 141	Novo Nordisk
EudraCT no.: 2014-001215-39		Page:	56 of 141	

Subjects will be instructed in how to record the results of the self-measured blood glucose (SMBGs) in the e-diaries. The record of each SMBG will include date, time point (e.g. before breakfast, before lunch, etc.) and value. BG should always be measured when a hypo- or hyperglycaemic episode is suspected. Hypoglycaemic and hyperglycaemic episodes will be recorded by the subject in the e-diary (see Section 8.6.3). The investigator may ask the subject to perform additional SMPG measurements if needed for any safety reason.

# 8.3.3 4-point self-measured plasma glucose profiles

Subjects will be instructed to perform SMPG measurements before breakfast, before lunch, before dinner and at bedtime daily to allow optimal insulin titration. The plasma glucose levels, the date and the time point of all measurements will be recorded for each time point stated in the e-diary.

# 8.3.4 7-point profile

Subjects will be instructed to perform SMPG measurements before and 90 minutes after the start of breakfast, lunch, dinner and at bedtime. Measurements will be performed according to the flowchart in Section  $\underline{2}$ . The plasma glucose levels, the date and the time point for all measurements will be recorded for each time point stated in the e-diary.

The 7-point plasma glucose profile includes one before breakfast measurement, one before lunch, one before dinner and one at bedtime measurement. These measurements are the same needed for the 4-point profile.

# 8.3.5 Insulin doses

Subjects will be instructed in how to record the insulin doses in the e-diaries. Each record should include date, time point (e.g. before breakfast, before lunch etc.), value, units and type (basal or bolus) of insulin.

Insulin doses will be collected on a daily basis to allow optimal insulin titration.

If a subjects reports an actual bolus insulin dose that deviates from the prescribed bolus insulin dose the subject will be asked to report a reason for this deviation in the e-diary.

# 8.3.6 Carbohydrate intake per meal

Subjects who will be titrated according to the principle of flexible insulin therapy (see Appendix A) will be instructed in how to record the carbohydrate intake in the e-diary. Each record should include date, time point (e.g. breakfast lunch etc.) and grams of carbohydrate. The carbohydrate intake will be collected on a daily basis, if applicable to allow optimal insulin titration.

Protocol		Date:	07 May 2015	Novo Nordisk
Trial ID: NN9828-4150	CONFIDENTIAL	Version:	2.0	
UTN: U1111-1154-7172	CONFIDENTIAL	Status:	Final	
EudraCT no.: 2014-001215-39		Page:	57 of 141	

#### 8.3.7 Patient reported outcomes (PROs)

The following questionnaires will be used in the trial to investigate the impact of the treatment on subject's overall health related quality of life and their treatment experience and satisfaction:

- 36-Item Short Form Health Survey version 2 (SF-36v2)
- Diabetes-Specific Health Beliefs: Experience of Treatment Benefits and Barriers Type 1 (ETBB)
- Diabetes Treatment Satisfaction Questionnaire status (DTSQs)

The questionnaires have to be completed by the subjects at selected visits (see Section  $\underline{2}$ ).

The questionnaires must be completed by the subject him/herself on paper and should preferably be completed after conclusion of all fasting activities but before any other visit-related activities. It will take the subject approximately 15 minutes to answer all the questions.

The questionnaires will be supplied in a linguistically validated version for all languages relevant for this trial.

It is the responsibility of the investigator or delegated staff to review the completed PRO questionnaires for (and ensure reporting of) any potential AEs. Review of PROs must be documented on the designated signature sheet on the documents and/or in the subject's medical record.

If clarification of entries or discrepancies in the PRO is needed, the subject must be questioned and a conclusion made in the subject's medical record. Care must be taken not to bias the subject

Data from the questionnaires will be transferred into the eCRF by the investigator or delegated staff.

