# 17 Statistical considerations

If necessary, a statistical analysis plan (SAP) may be written in addition to the protocol, including a more technical and detailed elaboration of the statistical analyses. The SAP will be finalised before database lock.

Based on the statistical model, treatment means or geometric means (LSMeans) and treatment comparisons (i.e. treatment differences or treatment ratios) will be presented with 95% confidence intervals (CI) and p-values for the two-sided test of no treatment difference. A significance level of 5% will be used. All pairwise treatment differences (or ratios) will be presented. No adjustment for multiple testing will be performed.

Some endpoints will be summarised for the treatment period, for the observation period and for the entire trial period (i.e. the treatment period together with the observation period)

The treatment period and the observation period will be derived for completed subjects as

- The start of the treatment period will be the date of first trial product administration
- The end of the treatment period will be the day before the visit at week 54 (i.e. the day before visit 63)
- The start of the observation period will be the day after the end of the treatment period
- The end of the observation period will be the date of the last visit

For withdrawn subjects the date of last contact will be the maximum of the date of the last visit and the withdrawal date. The treatment period and the observation period will be derived for withdrawn subjects as

- The start of the treatment period will be defined as described for completed subjects
- The end of the treatment period will be as defined for competed subjects if this date is before or on the date of last contact. Otherwise the end of the treatment period will be the date of last contact
- An observation period will only be defined if the date of last contact is after the end of the treatment period
  - The start of the observation period will be defined as for completed subjects
  - The end of the observation period will be the date of last contact

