#### 17.1 Sample size calculation

This is a phase 2 trial and the first Novo Nordisk trial of NNC0114-0006 in subjects with newly diagnosed T1DM. Therefore the knowledge on treatment effects and on the standard deviation of the primary endpoint is limited.

The statistical power calculations have been done under the following assumptions

- The primary endpoint is AUC0-4h for a MMTT stimulated C-peptide concentration-time curve at week 54 relative to baseline, i.e. AUC0-4h, C-peptide, 54w/AUC0-4h, C-peptide, baseline. The primary endpoint will be log-transformed in the statistical analysis and this will be denoted  $ln(AUC_{0-4h,C-peptide,\Delta54w})$ . Thus, AUC0-4h, C-peptide,\Delta54w is the proportion of AUCC-peptide that is preserved after 54 weeks relative to the level at baseline. E.g. a reduction of AUCC-peptide of 35% corresponds to a preservation of 65% and value of the  $ln(AUC_{0-4h,C-peptide,\Delta54w})$  is ln(0.65)=-0.431.
- The residual standard deviation of  $ln(AUC_{0-4h, C-peptide, \Delta 54w})$  in the model described above may depend on the treatment. Based on the results of Herold et al.  $\frac{40}{10}$  the standard deviation is assumed to be 1 in the placebo group and 0.5 in the group treated with NNC0114-0006 in combination with liraglutide.
- The expected preservation in the placebo treated patients is 65%, based on the results of Herold et al.  who found a mean of 70% decline in AUCC-peptide over a 24-months period. Assuming a linear decline, the mean 12-months decline would be 35%, i.e. a preservation of 65%. The statistical power calculations have been done assuming three levels of treatment effects for NNC0114-0006 in combination with liraglutide; a preservation of 85% and 95% and 98%, respectively.

Table 17–1 shows the statistical power for the test of no treatment effect if the true mean preservation is 85%, 95% or 98% in the group treated with NNC0114-0006 in combination with liraglutide and 65% in the placebo group when the numbers of completers are 40, 60 or 80, respectively using a two-sided test and 5% level of significance. The rows corresponding to the chosen number of (completing) subjects are highlighted.

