## Table 17–1Power calculations

Assuming a preservation of 98% and a SD of 0.5 for NNC0114-0006 in combination with liraglutide and a preservation of 65% and a SD of 1 for placebo, then the power will be 80.4% with 60 subjects completing the trial in each of the two treatment arms.

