#### Secondary objectives

Objectives related to treatment period (from baseline (week 0) to week 54):

- To assess safety and tolerability of NNC0114-0006 and liraglutide in combination and alone in subjects with newly diagnosed T1DM
- To assess effect on glycaemic parameters (including insulin usage and insulin regimen) of NNC0114-0006 and liraglutide in combination and alone in subjects with newly diagnosed T1DM
- To assess pharmacokinetic (PK) properties of NNC0114-0006 and liraglutide in combination and alone in subjects with newly diagnosed T1DM
- To explore biomarkers relevant for the effect of NNC0114-0006 and liraglutide in combination and alone in subjects with newly diagnosed T1DM
- To assess disease burden and health status in subjects with newly diagnosed T1DM treated with NNC0114-0006 and liraglutide in combination and alone

Objectives related to the post-treatment observation period (from week 54 to week 80):

- To assess post-treatment safety and tolerability of NNC0114-0006 and liraglutide in combination and alone in subjects with newly diagnosed T1DM
- To assess post-treatment effect on preservation of beta-cell function of NNC0114-0006 and liraglutide in combination and alone in subjects with newly diagnosed T1DM
- To assess post-treatment effect on glycaemic parameters (including insulin usage and insulin regimen) of NNC0114-0006 and liraglutide in combination and alone in subjects with newly diagnosed T1DM
- To explore biomarkers relevant for the post-treatment effect of NNC0114-0006 and liraglutide in combination and alone in subjects with newly diagnosed T1DM

- To assess post-treatment development of disease burden and health status in subjects with newly diagnosed T1DM treated with NNC0114-0006 and liraglutide in combination and alone

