### 1.1.2.2 Supportive secondary endpoints

#### Supportive secondary efficacy endpoints

- $AUC_{0-4h}$  for MMTT stimulated C-peptide concentration time curve at week 80 relative to baseline\*
- $AUC_{0-2h}$  for MMTT stimulated C-peptide concentration time curve at week 54 and week 80 relative to baseline\*
- Maximum MMTT stimulated C-peptide concentration ( $C_{max, C-peptide}$ ) at week 54 and week 80 relative to baseline\*
- $AUC_{0-4h}$  for MMTT stimulated plasma glucose concentration time curve at week 54 and week 80 relative to baseline
- $AUC_{0-2h}$  for MMTT stimulated plasma glucose concentration time curve at week 54 and week 80 relative to baseline
- Maximum MMTT stimulated plasma glucose concentration ( $C_{max, glucose}$ ) week 54 and week 80 relative to baseline
- Change in total daily insulin dose in units per kg (three day average) from baseline to week 54 and week 80\*
- Change in number of insulin injections per day (three day average) from baseline to week 54 and week 80
- Number of weeks off bolus insulin from baseline to week 54 and week 80
- Change in  $HbA_{1c}$  from baseline to week 54 and week 80\*
- Change in fasting plasma glucose from baseline to week 54 and week 80\*
- Change in fasting C-peptide from baseline to week 54 and week 80\*
- Change in fasting glucagon from baseline to week 54 and week 80
- 7-point self-measured plasma glucose (SMPG) profiles. The following endpoints will be derived:

- 7-point profiles at week 54 and week 80
- Change in postprandial glucose (PPG)/prandial increment (breakfast, lunch, dinner and average over the three meals) from baseline to week 54 and week 80
- Change in mean of 7-point profiles from baseline to week 54 and week 80
- Before breakfast SMPG at week 54 and week 80
- Change in patient reported outcome (PRO) scores (SF36, Experience of Treatment Benefits and Barriers, Diabetes Treatment Satisfaction Questionnaire (DTSQ)) from baseline to week 54 and week 80

\* Key supportive secondary endpoint prospectively selected for disclosure (e.g. clinicaltrials.gov and EudraCT)

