### **PRO endpoints**

Data collected with the PRO questionnaires (SF-36v2, Experience of Treatment Benefits and Barriers, and DTSQ (status)) will be scored according to the instruments' respective scoring algorithms into the following endpoints (domains)

- For Experience of Treatment Benefits and Barriers:
  - 'Perceived benefits'
  - 'Perceived barriers'
- For Diabetes Treatment Satisfaction Questionnaire (status):
  - 'Treatment satisfaction'
  - 'Perceived frequency of hypoglycaemia'
  - 'Perceived frequency of hyperglycaemia'
- For SF-36v2:
  - 'Physical Component Summary' score
  - 'Mental Component Summary' score
  - 'Physical functioning'
  - 'Role-physical'
  - 'Bodily pain'
  - 'General health'
  - 'Vitality'
  - 'Social functioning'
  - 'Role-emotional'
  - 'Mental health'

The PRO endpoints will be summarised using descriptive statistics.

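### PRO scores are collected to show the impact of treatment, but neither document plans a baseline-adjusted arm difference with a confidence interval for any of them

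*Protocol*

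**What the plan says.** Protocol 8.3.7 introduces SF-36v2, the Experience of Treatment Benefits and Barriers questionnaire and the DTSQs with a stated purpose: "The following questionnaires will be used in the trial to investigate the impact of the treatment on" health-related quality of life and on how subjects experience and rate their treatment. SAP 1.1.1 carries a matching secondary objective: "To assess disease burden and health status in subjects with newly diagnosed T1DM treated with NNC0114-0006 and liraglutide in combination and alone". A parallel objective covers the observation period. SAP 1.1.2.2 lists "Change in patient reported outcome (PRO) scores" from baseline to weeks 54 and 80 among the supportive secondary efficacy endpoints, without the asterisk that marks key ones.

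SAP 2.4.1.1 names 15 PRO domains (2 + 3 + 10) and then gives the whole analysis in one sentence: "The PRO endpoints will be summarised using descriptive statistics". Protocol 17.4.1.1 has the same sentence, and Protocol 17.7 only refers back to it. The list of changes in SAP section 3 does not mention PROs.

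Protocol 17 and SAP section 2 set the general rule for comparisons: all pairwise treatment contrasts with 95% CIs and two-sided p-values, no multiplicity adjustment, and "A significance level of 5% will be used". That rule is tied to results from a statistical model.

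**The concern.** The stated purpose is to learn what treatment does to patient-reported outcomes, and the endpoint is a change score measured in four randomised arms. The planned output stops short of a treatment-effect estimate. There is no model, arm contrast, confidence interval or baseline adjustment, and no statement on missing PRO data.

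Other continuous change endpoints at the same supportive level are treated differently, and no reason is given. What is at stake is how well the PRO results can be read. Readers would compare arm summaries by eye, or build their own unadjusted contrast. Any model added after the sponsor is unblinded at the week-54 database lock would be a post hoc choice among 15 domains.

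**Working it through.** **1. The planned analyses side by side (SAP 2.4.1.1 and 2.4.1.2)**

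| Endpoint (change from baseline) | Planned analysis | Arm difference with 95% CI |
|---|---|---|
| HbA1c, FPG | MMRM with baseline covariate | yes |
| Prandial increment, 7-point mean | same | yes |
| Biomarkers | same | yes |
| Body weight | same | yes |
| PRO scores, 15 domains | descriptive | none planned |

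**2. Do the PRO data fit that model?** Both flow charts schedule the questionnaires at Visit 3 (baseline), Visit 31 (week 24), Visit 63 (week 54) and Visit 89 (week 80). SAP section 2 already allows weeks 24, 54 and 80 in the MMRM. The data structure fits.

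**3. Numbers per arm.** Protocol 6.1 plans 304 randomised and 240 reaching the primary endpoint.
- Randomised per arm: 304/4 = 76. Expected to reach week 54 per arm: 240/4 = 60.
- Expected non-completion: (304 − 240)/304 = 64/304 = 21%.

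The figure of 60 is the one behind the plan's power statement, which reproduces. With 98% versus 65% preservation and log-scale SDs of 0.5 and 1, the difference is ln(0.98/0.65) = 0.411 and its standard error is √(1.25/60) = 0.144. A two-sided 5% test then has power 0.803 (noncentral t) or 0.812 (normal approximation), against 0.804 stated. There is no stated figure for PROs to reproduce.

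**4. Gain from baseline adjustment.** The documents give neither an SD nor a correlation for any PRO, so both are assumed: SD 10 at each visit, and correlation r between baseline and follow-up from 0.4 to 0.7.
- Variance of change: 2·SD²·(1 − r). Variance after baseline adjustment: SD²·(1 − r²).
- Ratio: (1 − r²)/(2(1 − r)) = (1 + r)/2.
- Standard error of an arm difference with 60 per arm: √(variance × 2/60).

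| r | Variance ratio | SE, raw change | SE, adjusted | SE reduction |
|---|---|---|---|---|
| 0.4 | 0.70 | 2.00 | 1.67 | 16% |
| 0.5 | 0.75 | 1.83 | 1.58 | 13% |
| 0.6 | 0.80 | 1.63 | 1.46 | 11% |
| 0.7 | 0.85 | 1.41 | 1.30 | 8% |

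The percentages do not depend on the assumed SD.

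**5. What a reader could already derive.** At r = 0.5 and 60 per arm, an unadjusted contrast of mean change has a 95% CI half-width of 0.36 outcome SDs. The adjusted contrast has 0.31.

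**6. Extra comparisons.** Five scores at weeks 54 and 80, with three active arms against placebo, give 5 × 2 × 3 = 30 contrasts. Under the all-pairwise rule the count would be 5 × 2 × 6 = 60.

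**The case against.** The case for leaving the plan alone has several sound parts.

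- **The documents agree with each other.** The SAP repeats the protocol's descriptive plan. A reader might infer that the SAP dropped a promised PRO analysis; it did not.
- **The objective is worded to assess.** Only the primary objective names a comparison with placebo. A reader might infer that the objective gets no usable estimate. That is too strong: descriptive change by randomised arm, with n, mean and SD, yields an unadjusted difference and interval.
- **The endpoint is within-subject change.** A reader might infer that different people are compared at baseline and week 54. A mean change uses both values from the same subject. Attrition affects who contributes, not the pairing.
- **The 21% is not PRO loss.** It is expected non-completion to week 54. Protocol 8.1.7 asks sites to aim for Visit 63-type procedures at withdrawal during treatment, and Visit 63 includes the questionnaires. Expected PRO missingness is not stated.
- **The model would not rescue early withdrawals.** Liraglutide escalation is scheduled to finish at Visit 10 (week 4), and Protocol 18.1 says gastrointestinal events are most frequent early. A subject withdrawn before week 24 with no post-baseline score contributes nothing to the model. The MMRM also relies on data being missing at random. A claimed direction of bias between arms would be speculation.
- **Other endpoints are descriptive too**, such as insulin injections, weeks off bolus insulin and 7-point profiles. The trial was sized for one comparison.

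All of this limits the point. It does not explain why an endpoint meant to show treatment impact, with its own objective and suitable repeated data, gets no planned effect estimate. SAP section 2 permits supplementary analyses but commits to none for PROs.

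**Conclusion.** The point holds as a minor, worthwhile improvement. Neither document plans a baseline-adjusted arm difference or 95% CI for any PRO, although the stated purpose is to investigate treatment impact and comparable change endpoints have such an estimate.

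The main gain is a pre-specified estimate with an interval. The secondary gain is precision: 15% to 30% lower variance than raw change, or a standard error about 8% to 16% lower. This rests on an assumed baseline correlation of 0.4 to 0.7 and equal variance at the two visits, neither of which the documents give.

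The documents do not support reading this as an error in the plan, as a contradiction between protocol and SAP, or as a cure for dropout bias.

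**What to change.** In SAP 2.4.1.1, PRO endpoints:

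- Analyse change in five main scores with the HbA1c model: DTSQs treatment satisfaction, perceived benefits, perceived barriers, and the SF-36v2 physical and mental component summaries. Use weeks 24, 54 and 80, with treatment, stratum, sex, age and baseline score, each by visit.
- Present differences versus placebo with 95% CIs, labelled supportive. State that for these scores this replaces the all-pairwise, p-value presentation in SAP section 2.
- Say how scores collected at withdrawal visits enter the model, in particular whether a Visit 63-type assessment done early counts as week 54. State the missing-at-random assumption.
- Keep the other ten domains descriptive.

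The cost is a paragraph of SAP text and a supportive table from a model already specified, settled before the week-54 database lock. The downside is 30 further contrasts without multiplicity adjustment, which is why they should be read as estimates and not as tests.
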